6 STUDY ENDPOINTS

6.1.1 Safety Endpoints

Safety endpoints include physical examinations, vital signs, clinical safety laboratory parameters, 12-lead ECGs, and adverse events.

6.1.2 Efficacy Endpoints

The efficacy endpoints are the following:

- Time (weeks) to decrease of BKV plasma viral load by 1 log;
- Time (weeks) to first decrease of BKV plasma viral load to <LLOQ;
- Time (weeks) to first decrease of BKV plasma viral load to <LOD;
- Proportion of subjects with ≥ 1 log decrease of BKV plasma viral load by 1 week, 2 weeks, 4 weeks, 8 weeks, 12 weeks, 16 weeks and 36 weeks;
- Proportion of subjects with decrease BKV plasma viral load to <LLOQ by 1 week, 2 weeks, 4 weeks, 8 weeks, 12 weeks, 16 weeks and 36 weeks;
- Proportion of subjects with decrease BKV plasma viral load to <LOD by 1 week, 2 weeks, 4 weeks, 8 weeks, 12 weeks, 16 weeks and 36 weeks;
- Rate of decrease in BKV plasma viral load over time by 1 week, 2 weeks, 4 weeks, 8 weeks, 12 weeks, 16 weeks and 36 weeks;
- Change in eGFR from baseline to week 12, baseline to week 16 and from baseline to week 36;
- Proportion of subjects with BKV nephropathy at week 12, week 16 and 36;
- Proportion of subjects with graft failure at week 12, week 16 and 36;
- Proportion of subjects with acute rejection at week 12, week 16 and 36 ; and
- Proportion of subjects who have died at week 12, week 16 and 36.

6.1.3 Exploratory Endpoints

The exploratory endpoints include the following:

- Presence of anti-drug antibodies (ADA);
- Presence of genotypic resistance. Genotype resistance data will be described in a separate report;
- Association between BKV genotype and outcome; and
- Viral kinetics of BKV in plasma and urine including rate of decrease in BKV urine viral load over time by 1 week, 2 weeks, 4 weeks, 8 weeks, 12 weeks, 16 weeks and 36 weeks.

6.1.4 Pharmacokinetic Endpoints

The pharmacokinetic endpoints include the following:

- MAU868 serum concentrations and the pharmacokinetic parameters estimated from them.

7 STATISTICAL METHODOLOGY

7.1 General Considerations

7.1.1 Analysis Day

Analysis day will be calculated from the date of first dose of study drug. The day of the first dose of study drug will be Day 1, and the day immediately before Day 1 will be Day -1. There will be no Day 0.

7.1.2 Analysis Visits

Scheduled visits will be assigned to analysis visits as recorded on the CRF.

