3 STUDY DESCRIPTION

3.1 Summary of Study Design

This is a randomized, placebo-controlled, blinded, proof-of-concept study in kidney transplant recipients. Up to 36 subjects with BK viremia will participate in 1 of 3 sequential cohorts. Each cohort will randomize approximately 12 subjects (8 MAU868 and 4 placebo). The study will consist of a Screening period (pre-treatment) of up to 10 days, a treatment period of 12 weeks and a follow-up period of 24 weeks.

Protocol specific procedures should not be performed until the subject has consented to participation in the study. However, assessments and procedures performed as part of standard of care prior to informed consent, including determination of BK viral load in plasma may be used to qualify a subject for the study. Once qualifying BK viremia has been confirmed, subjects should be randomized as soon as possible and no more than 10 days after the sample documenting the viremia was collected.

[figure not shown]
MAU868 or placebo will be administered approximately every 28 days (every 4 weeks) for 12 weeks (4 doses total). Urine and blood will be monitored for BKV DNA by PCR weekly for the first 6 weeks after initiation of treatment. For the remainder of the treatment period, urine and blood must be collected for BKV DNA by PCR at least every other week. PK, viral resistance and anti-drug antibodies will also be monitored. However, the Investigator may also request testing more frequently (i.e., weekly) than mandated by the protocol after the first 4 weeks of treatment when clinically indicated. During the study, BKV DNA by PCR will be tested at the central laboratory. Subjects should continue study drug until the last scheduled dose, regardless of changes in plasma BK viral load, use of rescue therapy and/or need for change in immunosuppressive regimen for any reason.

During the 24-week follow up period, 3 follow up visits will be scheduled at 4, 8 and 24-weeks post-treatment. At each visit, urine and blood samples for BKV DNA and samples for PK will be collected. Investigators may collect samples for BKV DNA more often as clinically indicated. During the follow-up period, BKV DNA by PCR will be tested at the central laboratory.

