In the case of discontinuation from study drug, subjects should be considered to have completed the treatment period and should complete the assessments required in the follow-up period (see [Appendix A](#)). Although the actual study days will vary between subjects and will not align with protocol-defined visit study days, time from last study dose remains the same (i.e., subjects will be seen approximately every 28 days for 2 follow up visits and then once again approximately 24 weeks after the last study dose). If the subject cannot be seen on the precise protocol-defined study day, the acceptable visit window is ± 10 days.

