7.4 Follow-up Period (Day 112 to Day 252)

Subjects will be seen approximately every 28 days for 2 follow up visits and then once again approximately 24 weeks after the last study dose. If the subject cannot be seen on the precise protocol-defined study day, the acceptable visit window is ± 10 days.

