8 STUDY PROCEDURES AND ASSESSMENTS

8.1 Schedule of Events

Subjects should be seen for all visits/assessments as outlined in the assessment schedule or as close to the designated day/time as possible.

Missed, late, or rescheduled visits should not lead to automatic discontinuation from the study.

Subjects who prematurely discontinue study drug should remain in the study. In the case of premature discontinuation from study drug, subjects should be considered to have completed the treatment period and should complete the assessments required in the follow-up period (see [Appendix A](#)). Although the actual study days will vary between subjects and will not align with protocol-defined visit study days, time from last study dose remains the same (i.e., subjects will be seen approximately every 28 days for 2 follow up visits and then once again approximately 24 weeks after the last of study dose received). If the subject cannot be seen on the precise protocol-defined study day, the acceptable visit window is ± 10 days.

Subjects who prematurely discontinue the study for any reason should be scheduled for a final study visit as soon as possible, at which time all of the assessments listed for the Early Termination Visit will be performed. At this final visit, all investigational product should be reconciled, and the adverse event and concomitant medications recorded on the eCRF and the reason for discontinuation of study documented. (See [Appendix A](#), Schedule of Events).

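### SAP 7.1.2 assigns visits by CRF label, so follow-up samples from subjects who stop drug early are analysed under visits 28 to 83 days later than they were taken

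*SAP*

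**What the plan says.** SAP 7.1.2 is one sentence: "Scheduled visits will be assigned to analysis visits as recorded on the CRF". SAP 7.1.1 states that "Analysis day will be calculated from the date of first dose of study drug", but the SAP never uses that day to place a result in a visit. It gives no visit windows, and no rule for follow-up visits after an early stop, Early Termination (ET) visits or unscheduled samples.

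Protocol 3.3.2 says that after discontinuation of drug "subjects should be considered to have completed the treatment period and should complete the assessments required in the follow-up period", and that "subjects will be seen approximately every 28 days for 2 follow up visits and then once again approximately 24 weeks after the last study dose". Protocol 8.1 repeats this and accepts that "the actual study days will vary between subjects and will not align with protocol-defined visit study days".

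The schedule of events (Protocol Appendix A, SAP Table 1) fixes FU1, FU2 and FU3 at Weeks 16, 20 and 36, Days 112, 140 and 252. ET shares the FU3 column.

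SAP 7.1.5 fills missing viral load at each scheduled visit by LOCF, and SAP 7.5.1.8 applies LOCF to eGFR at Weeks 12, 16 and 36.

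**The concern.** The protocol times these follow-up visits from the last dose. The efficacy endpoints are defined by weeks from baseline. For a subject who receives all four doses the two clocks agree. For one who stops early they do not, and the SAP follows the visit label.

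Two errors follow. A sample is analysed under a later week than the one in which it was taken. The week in which it was taken then looks empty and is filled from an older value, although a real result exists.

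Week 12 matters most. It is a timepoint of the second interim analysis (SAP 8.2.2), whose conclusions may lead to a change in the Cohort 3 regimen (SAP 8.2). With 8 subjects per active group, a few misplaced results can shift a by-visit summary.

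**Working it through.** **Inputs.** Doses are given on Days 1, 28, 56 and 84 (schedule of events). Follow-up visits fall 28, 56 and 168 days after the last dose (Protocol 3.3.2; Protocol 3.1 gives 4, 8 and 24 weeks). Nominal follow-up days are 112, 140 and 252.

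**Formula.** Actual follow-up day = last-dose day + 28, 56 or 168. Days early = nominal day − actual day.

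**The plan's own figures.** Last dose on Day 84 gives 84 + 28 = 112, 84 + 56 = 140 and 84 + 168 = 252, an exact match.

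**Early stops.**

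| Last dose | FU1 (nominal 112) | FU2 (nominal 140) | FU3 (nominal 252) | Days early |
|---|---|---|---|---|
| Day 56 | 84 | 112 | 224 | 28 (4.0 weeks) |
| Day 28 | 56 | 84 | 196 | 56 (8.0 weeks) |
| Day 1 | 29 | 57 | 169 | 83 (11.9 weeks) |

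A visit at the early edge of its ±10-day window adds 10 days, so the maximum is 83 + 10 = 93 days (13.3 weeks).

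**Which viral-load sample is used.** This assumes visits at their target days and no unscheduled samples. The by-day columns apply LOCF on analysis day.

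| Last dose | Week 12, by label | Week 12, by day | Week 16, by label | Week 16, by day | Week 36, either rule |
|---|---|---|---|---|---|
| Day 56 | Day 56 or 70, carried | Day 84 | Day 84 | Day 112 | Day 224 |
| Day 28 | Day 42 or earlier, carried | Day 84 | Day 56 | Day 84, carried | Day 196 |
| Day 1 | Day 21 or earlier, carried | Day 57, carried | Day 29 | Day 57, carried | Day 169 |

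In the first row the label rule sends the Day 84 sample to Week 16 and the Day 112 sample to Week 20. Week 20 is not an efficacy timepoint, so the real Week 16 result is not used at Week 16. Safety chemistry is not drawn on Day 70, so Week 12 eGFR for that subject would be carried from Day 56.

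The same displacement empties Week 8 after a last dose on Day 28, and Weeks 4 and 8 after a last dose on Day 1. Because only post-baseline values are carried, a one-dose subject with no treatment-period sample would have nothing to carry into those weeks.

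**Rate of decrease (SAP 7.5.1.7).** The formula does not say whether elapsed time is actual or nominal. On nominal time, a one-dose subject's FU1 change over 29 − 1 = 28 days (4 weeks) would be divided by 16, giving 4/16 = one quarter of the actual rate.

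**ET visits.** If the CRF stores ET under FU3/ET, an ET visit on Day 84 is filed (252 − 84)/7 = 24 weeks late, and one on Day 28 is filed (252 − 28)/7 = 32 weeks late.

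**Weight of one subject.** 1/8 = 12.5% of an active group; 1/12 = 8.3% of pooled placebo.

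**The case against.** The strongest reply concerns Week 36. A reader might infer that the durability result suffers most, since FU3 can be 83 days early and an ET visit far more. The documents do not support that. With LOCF in place, the last available value is the FU3 or ET result under either rule, so the Week 36 value, change and responder status stay the same unless a later sample exists. This part of the reply stands.

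The gain at Week 16 is also partial. For a one-dose subject the value used moves from 83 days early to 112 − 57 = 55 days early. That stands too.

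Much of the analysis is out of reach. Time-to-event endpoints use dates from first dose. Nephropathy, graft failure, rejection and death are counted as events by a given week. The responder rule in SAP 7.5.1.4 to 7.5.1.6 takes the latest result up to the timepoint, which can be read on analysis day; those proportions are exposed only if it is read by nominal visit.

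Timing from the last dose is deliberate: the visit days "will not align with protocol-defined visit study days, time from last study dose remains the same". That suits pharmacokinetics and time-off-drug summaries. It does not answer the point for endpoints defined from baseline.

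Finally, the CRF and the separate programming specifications (SAP 10) are not available, and Protocol 7.4.4 describes ET as a visit of its own. The labelling is therefore an inference, stronger for FU1 to FU3 than for ET. The specifications might add windows, but the SAP as written does not.

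**Conclusion.** The point holds for results between Weeks 4 and 16. Followed as written, SAP 7.1.2 files follow-up samples of early stoppers 28, 56 or 83 days late for a last dose on Day 56, 28 or 1, and replaces real results near Weeks 4, 8 and 12 with older carried values. It reaches by-visit viral load and its change, rate of decrease, eGFR at Weeks 12 and 16, by-visit safety summaries and the Week 12 second interim.

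The conclusion assumes that the CRF records these visits as FU1, FU2 and FU3, and that no windowing rule exists elsewhere. It also assumes that the sample is not already recorded under a treatment visit, as could happen if the decision to stop is taken at a dosing visit.

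Two further readings go too far:
- A reader might infer a bias between arms, because some treatment-related events require drug to be stopped. No stopping rate is given overall or by arm, and Protocol 3.3.2 lists other reasons for stopping. Both the number of subjects affected and any imbalance are unknown.
- A reader might infer that every affected subject moves a proportion by 12.5 or 8.3 percentage points. That happens only if the misplaced sample and the correct one give a different responder status.

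The study is not powered for efficacy, which limits the consequence. The by-visit summaries still inform decisions.

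**What to change.** Rewrite SAP 7.1.2 as follows:
- Assign all central-laboratory results (scheduled, follow-up, ET and unscheduled) to analysis visits by actual analysis day from first dose, taking the result closest to target within stated, non-overlapping windows. The protocol's visit windows would serve: ±3 days through Day 42, ±5 days for Days 56, 70 and 84, and ±10 days for Days 112, 140 and 252. They do not overlap: 39–45 is followed by 51–61, 65–75, 79–89, 102–122, 130–150 and 242–262.
- Apply LOCF and the responder rule on analysis day, so that results falling between windows can still be carried forward.
- Use actual elapsed time in the rate of decrease.
- Flag Week 36 values carried from before the Day 252 window. Days 169, 196 and 224 all fall before 242–262.
- Keep CRF labels for listings and for summaries by time since last dose.

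The cost is one SAP paragraph and one windowing step in programming, with no new data. The rule should be fixed before the unblinded second interim outputs are produced, so that the choice of which result counts as Week 12 is not made with results in view.

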7.1.3 Definition of Baseline

Baseline is defined as the last measurement prior to the first dose of study drug.

7.1.4 Summary of Statistics

Summary statistics will be presented by treatment group. The placebo subjects from the cohorts will be combined. For continuous variables, the number of observations (n), mean, standard deviation, median, minimum, and maximum will be provided. For categorical variables, the frequency and percentage in each category will be displayed.

For summary statistics, the mean and median will be displayed to one decimal place greater than the original value and the measure of variability (e.g. standard deviation) will be displayed to two decimal places greater than the original value.

All efficacy analyses will be conducted using two-sided tests at the alpha=0.05 level of significance, with no adjustment for multiplicity.

7.1.5 Handling of Dropouts and Missing Data

For Viracor/Eurofins BK viral load test results in both plasma and urine, the non-numerical results will be imputed as below in the analysis:

- ‘Detected:<39 copies/mL’ will be imputed as ‘38 copies/mL’ for plasma;
- ‘Detected:<61 copies/mL’ will be imputed as ‘60 copies/mL’ for urine;
- ‘Not Detected’ will be imputed as ‘25 copies/ mL’; and
- ‘>1.00E+10 copies/ mL’ will be imputed as ‘10¹⁰+1 copies/ mL’.

If there are multiple BK viral load test results for a single timepoint from both initial and back-up samples, the result from the back-up sample will be used in the analysis. If there are exceptions that require a different rule, it will be documented separately for the scenarios.

For Viracor/Eurofins BK viral load test results in both plasma and urine, missing data at each scheduled post-baseline visit will be imputed using the last post-baseline observation carried forward (LOCF) in the analysis.

Subjects who dropped out or had missing data will be included in the denominator for safety and efficacy analyses as described in Section 7.2.

In cases of missing or incomplete dates (e.g. Adverse event [AE] and concomitant medications), the missing component(s) will be assumed as the most conservative value possible. For example, AEs with missing start dates, but with stop dates either overlapping into the treatment period or missing, will be counted as treatment-emergent, taking the worst-case approach. When partial dates are present in the data, both a partial start date and/or a partial stop date will be evaluated to determine whether it can be conclusively established that the AE started prior to the start of study drug or ended prior to the start of study drug. If the above cannot be conclusively established based on the partial and/or present dates, then the AE will be considered as treatment-emergent. Actual data values as they appear in the original eCRF will be presented in the data listings.

Missing values for other variables will not be imputed and only observed values will be used in data analyses and summaries.

7.2 Analysis Populations

7.2.1 *Intent-to-Treat (ITT) Population*

The ITT Population includes all randomized subjects in the study.

7.2.2 *Modified Intent-to-Treat (MITT) Population*

The MITT Population includes subjects who had the disease under study (had renal transplant within the year with a graft that is currently functioning and have met the BK viremia protocol entry criteria [baseline BK PCR plasma viral load test result $\geq 10^3$ based on central laboratory data]), received at least 1 dose of study drug and have at least 1 post-baseline plasma BK viral load result available.

7.2.3 *Safety Population*

The Safety Population includes all subjects who received at least 1 dose of study drug.

7.2.4 *Pharmacokinetic (PK) Population*

The PK Population includes all subjects with at least 1 post-baseline PK sample available. A separate PK analysis plan will outline PK analyses.

7.3 Subject Data and Study Conduct

7.3.1 *Subject Disposition*

Subject disposition will be summarized by treatment group and in total for the ITT and MITT Populations. The following subject disposition categories will be included in the summary:

- Subjects who received study drug;
- Subjects who did not receive study drug;
- Subjects who completed the study drug;
- Subjects who did not complete the study drug (and reason);
- Subjects who did not complete the study drug due to the impacts of the COVID-19 pandemic;
- Subjects who completed the study;
- Subjects who did not complete the study (and reason); and
- Subjects who did not complete the study due to the impacts of the Covid-19 pandemic.

For subjects who did not complete study drug and subjects who did not complete study, a summary will be provided by reason of discontinuation. In addition, the total number of subjects for each defined analysis population will be tabulated.

Subject disposition will also be listed by treatment and subject.

7.3.2 Protocol Deviations

The number of subjects with at least one reportable protocol deviation, and the number of patients with at least one reportable deviation in each deviation category defined in the study protocol deviation plan will be presented by treatment group and in total based on the ITT and MITT Populations. In addition, the protocol deviations related to COVID-19 pandemic will be categorized and summarized separately.

Protocol deviations will also be listed by treatment and subject.

7.3.3 Demographic and Baseline Characteristics

The following demographic and baseline characteristics will be summarized:

- Age (years) and age categories (<65 years vs. ≥ 65 years);
- Sex;
- Race;
- Ethnicity
- Height (cm);
- Weight (kg);
- Body mass index (BMI) (kg/m^2) ;
- eGFR based on the CK-EPI equation ($\text{mL}/\text{min}/1.73\text{m}^2$) and eGFR categories (<15, 15-<30, 30-<60, 60-<90, and ≥ 90);
- Living donor (Yes vs. No);
- Pre-existing BKV nephropathy (Yes);

Note: Pre-existing BKV nephropathy can be identified based on the following CRF data:

- Medical history using the preferred term ‘Polyomavirus-associated nephropathy’; and
- Clinical outcome assessments indicating subjects developed or possibly developed BKV associated nephropathy at Baseline visit.

- Time from kidney transplant (days);

Time from kidney transplant (days) is calculated as the first dose date of study drug - date of kidney transplant;

- Baseline plasma viral load (copies/mL);
- Duration of BK viremia

Duration of BK viremia (days) is calculated as the first dose date of study drug - date of first reported BK plasma positive PCR

Note: the first reported BK plasma positive PCR is based on CRF data of Historical BKV Blood Sample Results and the quantitative result in copies/mL $\geq 10^3$.

- BKV genotype

Demographic and Baseline characteristics will be summarized with descriptive statistics or counts and percentages of subjects as appropriate for the ITT, MITT, and Safety Populations. Other parameters of Kidney donor profile index (KDPI) will be listed.

7.3.4 *Medical History*

Medical history will be coded to system organ class and preferred term using the Medical Dictionary for Regulatory Activities (MedDRA, Version 22.1). Counts and percentages of subjects with medical history by system organ class and preferred term will be summarized by treatment based on the ITT, MITT and Safety Populations.

All medical history will be listed by treatment and subject.

7.3.5 *Concomitant Medications*

Prior and Concomitant medications will be coded to anatomical therapeutic chemical (ATC) class and preferred term using the World Health Organization (WHO) Drug Dictionary (September 2019G B3).

Prior medications are medications used before the first dose of study drug. Concomitant medications are medications that were taken on or after first dose of study drug. Any medications used before first dose of study drug and continued will be counted as both prior and concomitant medications.

The number and percentages of patients who receive the following prior and concomitant medications will be summarized by ATC class and preferred term based on ITT, MITT, and Safety Populations:

- Prior medications;
- Concomitant medications;
- Prior immunosuppressive agents with dose decreased or discontinued due to BKV;
- Concomitant immunosuppressive agents with dose decreased or discontinued due to BKV;
- Prior immunosuppressive agents with clinically significant decrease in dose or discontinuation;
- Concomitant immunosuppressive agents with clinically significant decrease in dose or discontinuation.

All prior and concomitant medications will be listed by treatment and subjects.

Any clinically significant (based on blinded review of medical monitor) decrease in dose or discontinuation of prior or concomitant immunosuppressive medication will be described regardless of whether the reason was due to BKV or not.

7.3.6 *Study Drug Exposure*

All study drug will be administered by IV infusion. Days of exposure to study drug will be calculated as the last dose date of study drug – first dose date of study drug + 1. The days of exposure to study drug will be summarized based on the Safety and MITT Populations with

descriptive statistics and with counts and percentages of subjects with exposure in the following categories:

- ≤ 28 days
- >28 to ≤ 56 days
- >56 to ≤ 84 days
- >84 days

Total number of doses received will be summarized based on the Safety and MITT Populations with counts and percentages of subjects in the following categories: 1, 2, 3, and 4 doses.

